4 STATISTICAL ANALYSES

4.1 GENERAL CONSIDERATIONS

Due to early termination of the study, the analyses described in this SAP were not performed in totality due to lack of data and in accordance with the abbreviated CSR (clinical study report). See Appendix 2 ([Section 5.2](#)): Changes to protocol-planned analyses for additional details.

In general, continuous data will be summarized using the number of observations available, mean, SD, median, Q1, Q3, minimum, and maximum.

All mean, SD, median, Q1 and Q3 values will be formatted to one more decimal place than the measured value. Minimum and maximum will be formatted to the same number of decimal places as the measured value.

Categorical data will be summarized using frequency counts and percentage of participants. When count data are presented, the percent will be suppressed when the count is zero to draw attention to the non-zero counts. A row denoted 'Missing' will be included in count tabulations for demographics, baseline characteristics and compliance to account for missing values. No percentages will be displayed on the 'Missing' rows and the percentages on the other rows will be based on the number of non-missing observations. Unless otherwise specified, the denominator for all other percentages will be the number of participants in that treatment within the specific analysis set of interest. All percentages will be rounded to one decimal place. The number and percentage of responses will be presented in the form xx (xx.x), where the percentage is in the parentheses. When the numerator is equal to the denominator, the percentage should be presented as (100) instead of (100.0), unless otherwise specified.

All CIs presented will be 2-sided 95% CIs, unless otherwise specified, and will be displayed to the same level of precision as the statistic they relate to. If an estimate or a CI is not estimable, it will be presented as 'NE'. If neither an estimate, nor its CI are estimable, it will be presented as simply 'NE', not displaying 'NE' twice.

The p-values will be rounded to four decimal places. If a p-value is less than 0.0001 it will be reported as '<0.0001'. If a p-value is greater than 0.9999 it will be reported as '>0.9999'. The baseline value is defined as the last available non-missing value before the first injection of study drug (Gla-300 or IDeg-100). For participants randomized but not treated, the baseline value is defined as the last available non-missing value recorded before randomization occurs at the end of the screening period. Where time is collected, it will be included in the determination of baseline records. Any measurement or assessment recorded on the day of first dose administration of open-label IMP (or day of randomization for participants randomized but not treated) with missing assessment time will be considered as Baseline.

If multiple valid values of a variable (efficacy or safety) occur within the same day considered as Baseline (and the recorded times of measurement do not identify which of them is the latest assessment), the following rules will be considered:

- If only one of the multiple valid values was measured during a scheduled visit, it will be considered as Baseline in the analysis.

- If multiple values are measured during a scheduled visit within the same day, then these values will be averaged, and the average will be considered as Baseline for the analysis. If there are also values within the same day not collected during a scheduled visit, these will be excluded from the average.
- If no values measured within the same day were assessed during a scheduled baseline, then all measurements from that day will be averaged, and this value will be considered as Baseline for the analysis.

A stepwise closed testing approach will be used for the primary efficacy endpoint to assess non-inferiority and superiority sequentially.

- Step 1 will assess non-inferiority of Gla-300 versus IDeg-100. To assess non-inferiority, the 2-sided 95% CI of the difference in the mean change from baseline to Week 24 in HbA1c level between Gla-300 and IDeg-100 in the ITT population will be compared with the predefined non-inferiority margin of 0.3%. Non-inferiority will be demonstrated if the 2-sided 95% CI of the difference in the mean change from baseline to Week 24 in HbA1c level between Gla-300 and IDeg-100 lies entirely below 0.3% (equivalent to a 1-sided test at the 2.5% significance level).
- Step 2 will test superiority of Gla-300 versus IDeg-100 if noninferiority of Gla-300 versus IDeg-100 as described above has been demonstrated. The superiority of Gla-300 versus IDeg-100 will be established if the 95% CI for the difference in mean change from baseline to Week 24 in HbA1c level between Gla-300 and IDeg-100 lies entirely below 0%. If non-inferiority has been established but the superiority is not met, the declaration of non-inferiority will be further supported by a supplementary estimand as described in [Section 4.3.4](#).

There is no multiplicity argument that affects switching between non-inferiority and superiority in the analysis of the primary endpoint, since both are based on the same estimand and it therefore corresponds to a simple closed testing procedure. If superiority for the primary endpoint (change from baseline to Week 24 in HbA1c level) is achieved, secondary endpoints will be assessed for superiority and adjusted for Type I error related to multiple testing using the Holm procedure as described in [Section 4.6](#). Control of Type I error will be limited to the primary and key secondary efficacy endpoints for the overall population. No statistical claim will be made on the exploratory efficacy endpoints (including the CGM substudy endpoints), nor for subgroup analyses.

All safety analyses will be performed on the safety set.

In general, descriptive statistics of quantitative efficacy and safety parameters (result and absolute change from baseline) by analysis visits will be provided on observed cases (OC; ie, inclusion of only participants having non-missing assessments for a specific analysis visit). Descriptive summaries of continuous efficacy and safety data at baseline will be included when presenting descriptive summaries of the corresponding changes from baseline, where appropriate. Unless otherwise specified, analyses will be performed by intervention group (and overall for baseline and demographics characteristics).

Despite the open-label administration of the study drugs, all statistical analyses outlined in this plan prior to final database lock will be developed and performed blindly. A process will be

applied to ensure blinding of Gla-300 and IDeg-100 administrations and any potentially unblinding information.

All statistical analyses will be performed using SAS software Version 9.4 or higher.

Observation period

The observation period will be divided into 3 segments for non-safety analyses:

- The **pre-treatment period** (up to 2 weeks) is defined as the time between the date of signed informed consent and the first injection of the open-label study drug.
- The **on-treatment period** (24-weeks) is defined as the 24-week open-label treatment period. The on-treatment period includes a 12-week titration period where study drug doses will be adjusted using a recommended dose-adjustment algorithm, as well as a 12-week maintenance period at the titrated dose.
- The **post-treatment period** is defined as the 7-day, post-treatment, safety follow-up period after the last dose of the study drug or after premature/permanent discontinuation from study drug treatment.

The on-study period is defined as the time from the date of signed informed consent until the end of the study defined as the last scheduled visit for those who completed the study and the end-of-study date (“Status Date”) collected on electronic case report form (eCRF) page “Completion of End of Study” for those who did not complete the study. If death is the end-of-study reason, date of death will be used.

The observation period used for safety analyses is described in [Section 4.7](#).

The maximum trial duration per participant will be 27 weeks.

4.2 PARTICIPANT DISPOSITIONS

The number of participants included in each of the analysis populations listed in [Table 4](#) will be summarized. Percentages for the PP population and CGM Substudy population will be calculated using the ITT set as the denominator.

Screen failures are defined as participants who consent to participate in the study but are not subsequently randomized. The number of participants screened, the number (%) of screen failures, and number (%) of reason for screen failures will be summarized for the screened set.

The number (%) of participants in the following categories will also be provided, using the ITT (randomized population) as the denominator:

- Randomized and not exposed participants.
- Randomized and exposed participants.
- Participants who completed the 24-week study treatment period as per protocol.
- Participants who did not complete the 24-week study treatment period as per protocol and main reason for permanent intervention discontinuation.

- Participants who completed the study period as per protocol.
- Participants who did not complete the study period as per protocol and main reason for study discontinuation.

The number of exposed and not randomized participants will also be included in the summary above.

In addition, the number (%) of participants screened, screened-failed, randomized, randomized and exposed, with study drug discontinuation and with study discontinuation will be provided by country and site. For the number (%) of participants screened and screen-failed, the screened set will be used as a denominator; for the remaining summaries, the ITT set will be used as the denominator for percentages.

The number (%) of participants with trial impacts (disruptions) due to coronavirus disease 2019 (COVID-19) will also be summarized for the safety set. Participants for whom at least one of the following events occurred during the study will be presented:

- Permanent discontinuation of treatment due to COVID-19, defined as participants whose “Main Reason for Premature End of Treatment” on End of Treatment eCRF page is “Adverse Event”, and a corresponding adverse event (AE) of “Covid-19” with “Drug withdrawn” as the response to “Action Taken with Study Treatment” on the Adverse Events eCRF page.
- Permanent discontinuation of treatment due to AE related to COVID-19 infection, defined as participants whose “Main Reason for Premature End of Treatment” on End of Treatment eCRF page is “Adverse Event”, and a corresponding adverse event of “AE Term due to Covid-19” with “Drug withdrawn” as the response to “Action Taken with Study Treatment” on the Adverse Events eCRF page.
- Premature end of treatment due to COVID-19 pandemic, defined as participants whose “Main Reason for Premature End of Treatment” on the End of Treatment eCRF page is “Other”, and in “If Other, specify” beginning the Specify comment following text “Covid-19.”.
- Premature end of study due to COVID-19 pandemic, defined as participants whose “Subject Status” on the Completion of End of Study eCRF page is “Other”, and in “If Other, specify details” beginning the Specify comment following text “Covid-19.”.

Protocol deviations

Significant protocol deviations (automatic or manual), including drug dispensing irregularities, will be summarized for the ITT population. Protocol deviations due to the COVID-19 pandemic will be categorized as such. Protocol deviations will come from the clinical trial management system and will be categorized according to the rules document for protocol deviations. For the purpose of this analysis, significant deviations will be defined and reviewed on a case-by-case basis for each participant in a blinded data review meeting, where a significant protocol deviation is considered to be a deviation that affects primary efficacy and safety assessments (as applicable), the safety or mental integrity of a subject, or the scientific value of the trial. Only those protocol deviations impacting the primary endpoint will lead to exclusion from the Per Protocol Set.

4.3 PRIMARY ENDPOINT ANALYSIS

4.3.1 Definition of endpoint

The primary endpoint is the change from baseline to Week 24 in HbA1c level. For efficacy assessments of the trial, HbA1c will be measured with blood samples collected at the central laboratory at the time points specified in [Section 5.7](#) (baseline, Week 12, Week 24). If a participant needs to receive a rescue antidiabetic therapy, the HbA1c assessment should be performed before the antidiabetic therapy is introduced. In addition, in case of study drug treatment discontinuation, participants will be followed up per protocol. In case of trial discontinuation, HbA1c assessment will be performed at the time of withdrawal. If HbA1c measurements fall out of windowed assessments (baseline, Week 12, Week 24), the results for those assessments will be excluded (considered as missing for analysis).

4.3.2 Main analytical approach

The primary estimand is the difference in the mean change from baseline to Week 24 in HbA1c level (Gla-300 vs IDeg-100) in insulin-naïve participants with T2DM and renal impairment who have glycemic levels above target with OADs with or without GLP-1 RA (oral or injectable), regardless of discontinuation of study drug treatment due to any reason or use of rescue therapies (treatment policy strategy).

The statistical hypothesis associated with the primary non-inferiority analysis of change from baseline in HbA1c level to Week 24 is:

$$H_0: \mu_{Gla-300} - \mu_{IDeg-100} \geq 0.3\%$$

$$H_1: \mu_{Gla-300} - \mu_{IDeg-100} < 0.3\%$$

where $\mu_{Gla-300}$ and $\mu_{IDeg-100}$ denote the true mean change from baseline to Week 24 in HbA1c level for Gla-300 and IDeg-100, respectively.

If the non-inferiority is demonstrated, the hypothesis for testing superiority will be:

$$H_0: \mu_{Gla-300} - \mu_{IDeg-100} = 0\%$$

$$H_1: \mu_{Gla-300} - \mu_{IDeg-100} \neq 0\%$$

HbA1c data collected after ICEs (discontinuation of study drug treatment due to any reasons, use of rescue therapies) will be included in the analysis based on the ITT set. Missing data will be handled using a MI strategy dependent on treatment-completion status:

- Missing data from participants discontinuing the study drug treatment will be imputed using data from participants also discontinuing the study drug treatment but who have their endpoint assessed within each treatment arm.

- Missing data from participants completing the 24-week treatment period will be imputed using a model estimated from data observed in other participants completing the study drug treatment within each treatment arm.

The number (%) of participants for each missing pattern will be summarized by treatment group for the ITT set:

- Patients with non-missing baseline HbA1c data but without post-baseline HbA1c data.
- Patients with non-missing baseline and Week 12 HbA1c data who are missing Week 24 HbA1c data.
- Patients with non-missing baseline and Week 24 HbA1c data who are missing Week 12 HbA1c data.

The following two-step approach will be used for the MI:

- Step 1: The Markov chain Monte Carlo (MCMC) method will be used to impute intermediate missing data to create a monotone missing data pattern.
- Step 2: Using the 100 imputed datasets with monotone missing data pattern obtained from Step 1, missing data will then be imputed for each imputed data set using the sequential regression method.

The imputation model for Step 1 will be performed by randomized treatment arm and include baseline HbA1c value and HbA1c values at Week 12 and Week 24 and use SEED=17007. Step 1 will impute intermediate missing data to a monotone missingness pattern and create 100 imputed datasets (the SAS default of 1000 burn-in iterations for MCMC will be used when creating the 100 imputed datasets). The number of imputations may be increased if large variability of the results produced with increasing number of imputations before reaching 100 imputations is observed.

The imputation model for Step 2 will include the same variables as in Step 1, as well as randomization strata: SU use (Yes, No) and eGFR at Screening (<45 mL/min/1.73 m 2 ; \geq mL/min/1.73 m 2). Step 2 will be performed based on the imputed datasets in Step 1 with monotone missing pattern, and the model will use SEED=70071. If there is an insufficient number of participants with complete data within a randomization stratum for establishing the imputation model, some randomization stratification factors may be removed from the imputation model by combining groups together where needed. In the case that there is an insufficient number of patients who have discontinued treatment but have data available at Week 24 in either treatment arm for establishing the model, treatment arm may also be removed from the model, and missing data for patients discontinuing the study drug treatment will be randomly sampled from the normal distribution, using observed baseline value as the mean of the distribution.

After completing Step 2, an analysis of covariance (ANCOVA) model will be performed for each imputed data set; this analysis will include baseline HbA1c value as a covariate, study drug treatment, and randomization strata (SU use (Yes, No) and eGFR (<45 mL/min/1.73 m 2 ; \geq 45 mL/min/1.73 m 2) as fixed factors. Graphical methods will be used to check if there are major deviations from normality. The difference in mean change from baseline to Week 24 in HbA1c

values between treatment arms (Gla-300 vs IDeg-100) will be estimated based on the difference of LS means in the ANCOVA model. The estimated differences and associated standard errors (SEs) obtained across the imputed datasets will be combined via SAS PROC MIANALYZE to produce a single point estimate difference, corresponding SE, 2-sided 95% CI (Wald), and two-sided p-value for superiority, all based on Rubin's rules.

The test for non-inferiority will be performed at a 1-sided 2.5% significance level, and the non-inferiority will be demonstrated if the upper bound of the 2-sided 95% CI of the pooled difference in change from baseline to Week 24 in HbA1c values between Gla-300 and IDeg-100 treatment arms is <0.3%. Superiority will be established if the upper bound of the 2-sided 95% CI is <0%.

In addition, a box plot based of HbA1c from baseline to Week 24 (OC) will be produced.

4.3.3 Sensitivity analysis

Sensitivity analyses will be conducted for the ITT population to assess the robustness of the results obtained from the primary analysis described in [Section 4.3.2](#).

Mixed-Effect Model with Repeated Measurements

An MMRM analysis based on OC and assuming MAR will be carried out via SAS PROC MIXED; this sensitivity analysis will include randomized study drug treatment (Gla-300, IDeg-100), visit (Week 12, Week 24), and stratification factors at randomization (SU use (Yes, No) and eGFR ($<45 \text{ mL/min/1.73 m}^2$; $\geq 45 \text{ mL/min/1.73 m}^2$) as fixed factors, continuous baseline HbA1c value as a covariate, and treatment-by-visit and baseline HbA1c value-by-visit interactions. An unstructured covariance matrix will be used to model the within-participant errors. Graphical methods will be used to check if there are major deviations from normality. Parameters will be estimated using the restricted maximum likelihood method. The Kenward-Roger approximation will be used to estimate denominator degrees of freedom. In this analysis, no imputation of missing data will be performed. The difference in mean change from baseline to Week 24 in HbA1c between treatment arms (Gla-300 vs IDeg-100) will be estimated based on the baseline adjusted MMRM model. The estimates will be presented together with their corresponding SE, 95% CI and 2-sided p-value for superiority at Week 24.

Penalized MI (For Non-Inferiority Only)

Separately, penalized MI will be performed as an additional sensitivity analysis (for non-inferiority only). The multiply imputed missing HbA1c values at Week 24 in the primary analysis will be penalized by adding 0.3% (corresponding to the non-inferiority margin) to the imputed HbA1c value in the Gla-300 arm, whereas the imputed HbA1c in the IDeg-100 arm will not be penalized. Each imputed complete dataset will then be analyzed using the same ANCOVA as described for the primary analysis in [Section 4.3.2](#). The treatment differences and their SEs estimated from each imputed (penalized or not) dataset will be combined using Rubin's rules for a point estimate and presented with associated 2-sided 95% CI (Wald).

Reference-Based MI (For Superiority Only)

Reference-based MI assuming missing not at random (MNAR) pattern of missingness will also be performed (for superiority only). The reference-based MI approach will assume that the trajectory of withdrawals from the Gla-300 arm due to any reason is the same as that in the IDeg-100 arm. Following the completion of Step 1 (impute to monotone step) as described in the primary analysis approach in [Section 4.3.2](#), missing Week 12 HbA1c values and Week 24 HbA1c values in the Gla-300 arm will then be imputed using a sequential regression imputation model established using data in the IDeg-100 arm. Each imputed complete dataset will be analyzed using the same ANCOVA as described for the primary analysis in [Section 4.3.2](#). The treatment differences and their SEs estimated from each imputed dataset will then be combined using Rubin's rules for a point estimate and presented with associated two-sided p-value for superiority and 2-sided 95% CI (Wald).

4.3.4 Analysis of supplementary estimand (For non-inferiority only)

An analysis will also be performed to estimate the supplementary estimand. It will be performed for the ITT population to support non-inferiority only. For this analysis, data collected after discontinuation of study drug treatment due to any reasons or after use of rescue therapies will be excluded in the analysis of change from baseline to Week 12 and Week 24 in HbA1c level (Gla-300 vs IDeg-100) (hypothetical strategy).

An MMRM based on OC and assuming MAR will be performed for the change from baseline in HbA1c values at Week 12 and Week 24, and it will include study drug treatment, visit, and stratification factors at randomization (other than categorized Hb1Ac) as fixed factors, baseline HbA1c value as a covariate and treatment-by-visit and baseline HbA1c value-by-visit interactions. Graphical methods will be used to check if there are any major deviations from normality. An unstructured covariance matrix will be used to model the within-participant errors. Parameters will be estimated using restricted maximum likelihood method. The Kenward-Roger approximation will be used to estimate denominator degrees of freedom. Least-squares means, differences, and associated SEs will be presented with 2-sided 95% CIs.

4.3.5 Supportive analysis of supplementary estimand (For non-inferiority only)

As a supportive analysis of the supplementary estimand, a per-protocol analysis based on the PPS will be performed for non-inferiority. An MMRM assuming MAR will be performed as described for the primary analysis in [Section 4.3.3](#). Least-squares means, differences, and associated SEs will be presented with 2-sided 95% CIs. The analysis will also be repeated for the ITT set.

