8.7.3.4 Supportive Analysis of Supplementary Estimand

A per-protocol analysis based on the PPS will be performed as a supportive analysis for non-inferiority. An ANCOVA will be performed as described for the primary analysis. No imputation of missing data will be needed, as patients with missing Week 24 measurements will be excluded from the PPS.

[figure not shown]

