3 ANALYSIS POPULATIONS

The following populations for analyses are defined:

Table 4 - Populations for analyses

Population	Description	Analyses
Screened	All participants who signed the informed consent form (ICF).	Participant disposition analyses.
Safety	All randomized participants who receive at least 1 dose of study drug treatment. All analyses using the safety set will be done according to the treatment actually received.	Safety analyses.
Intent-to-treat (ITT)	All participants who sign the ICF and are randomized into the trial. All analyses using the ITT set will group participants according to their randomized treatment.	Primary endpoint analyses (including subgroup analyses), secondary endpoints analyses, exploratory endpoints analyses not related to the CGM substudy, demographics analyses, baseline characteristic analyses, participant disposition analyses.
Per-protocol (PP)	All randomized participants who complete the trial without significant protocol deviations impacting the primary endpoint.	Supportive analysis of the primary endpoint analysis.

CCI

Participants exposed to study intervention before or without being randomized will not be considered randomized and will not be included in any analysis population. The safety experience of these participants will be reported separately.

Randomized participants for whom it is unclear whether they took the study intervention will be considered as exposed and will be included in the safety population as randomized.

For any participant randomized more than once, only the data associated with the first randomization will be used in any analysis population. The safety experience associated with any later randomization will be reported separately.

For participants receiving more than one study intervention during the study, the intervention group for as-treated analyses will be the as-randomized intervention group if the participant has received at least one administration of the as-randomized intervention.

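### SAP 4.3.5 labels the per-protocol analysis as support for the hypothetical estimand but refers its model to the treatment-policy MMRM of 4.3.3, so HbA1c after rescue, and in some patients after stopping study drug, is not excluded

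*SAP*

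**What the plan says.** SAP 4.3.5 states its purpose in its first sentence: "As a supportive analysis of the supplementary estimand, a per-protocol analysis based on the PPS will be performed for non-inferiority". The supplementary estimand (1b, SAP Table 3) is hypothetical: it asks what the HbA1c difference would be with no discontinuation of study drug and no rescue. The data rule that goes with it is in SAP 4.3.4, where "data collected after discontinuation of study drug treatment due to any reasons or after use of rescue therapies will be excluded"; Table 3, note b, says the same.

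For its model, 4.3.5 does not point to 4.3.4. It says "An MMRM assuming MAR will be performed as described for the primary analysis in" Section 4.3.3, and then adds "The analysis will also be repeated for the ITT set".

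Section 4.3.3 opens with "Sensitivity analyses will be conducted for the ITT population to assess the robustness of the results obtained from the primary analysis described in" Section 4.3.2. Its model is introduced as "An MMRM analysis based on OC and assuming MAR will be carried out via SAS PROC MIXED". It gives no rule removing values after an intercurrent event. The primary analysis in 4.3.2 is multiple imputation with ANCOVA, and it includes such values.

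The per-protocol population in SAP Section 3 is "All randomized participants who complete the trial without significant protocol deviations impacting the primary endpoint". In the protocol (8.7.3.4), the same supportive analysis was to be different: "An ANCOVA will be performed as described for the primary analysis".

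**The concern.** A supportive analysis is useful only if it targets the estimand it is said to support. The hypothetical estimand was added because, in a non-inferiority comparison, rescue and stopping can make two arms look more alike than the drugs are. If the supporting per-protocol analysis keeps the values recorded after those events, agreement between it and 4.3.4 could be read as corroboration when the two analyses answer different questions.

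Two smaller matters follow from the same sentences. The ITT repeat adds no information, so one result could appear under two labels. The change of model from the protocol's ANCOVA to an MMRM is not listed in SAP Appendix 2, although protocol Section 8 says that changes from the planned analyses will be documented in the SAP.

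**Working it through.** **1. Where the reference leads**

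| SAP section | Model | Estimand served | HbA1c after discontinuation or rescue |
|---|---|---|---|
| 4.3.2 | MI + ANCOVA, ITT | 1a, treatment policy | included |
| 4.3.3 | MMRM, observed cases, ITT | sensitivity of 1a | no exclusion stated |
| 4.3.4 | MMRM, observed cases, ITT | 1b, hypothetical | excluded |
| 4.3.5 | MMRM as in 4.3.3, per-protocol set, then ITT | labelled support for 1b | no exclusion stated |

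The MMRMs in 4.3.3 and 4.3.4 have the same fixed effects, interactions, unstructured covariance, REML and Kenward-Roger. They differ in the data rule, and that rule is what the reference to 4.3.3 loses.

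**2. Whether the per-protocol set restores the rule**

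- Rescue: protocol 5.2.2 keeps the rescued patient in the trial, on study drug, with planned visits to the end, and protocol 5.11 permits rescue. Rescue as such is therefore no bar to completing the trial.
- Which value is used: the rescue thresholds apply after Week 12, and HbA1c is scheduled only at Weeks 12 and 24 after baseline. A sample before rescue is requested, but SAP 5.4.5.1 takes the value closest to Day 169 for Week 24. A scheduled post-rescue Week 24 value will normally be the one analysed.
- Stopping drug: protocol 4.4.1.1 follows these patients to scheduled trial completion, so some can complete the trial off drug. Those who leave the trial are not in the set. For the rest, SAP 4.2 decides exclusion case by case at blinded deviation review.

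**3. The ITT repeat.** As written, it is the 4.3.3 MMRM in ITT, which 4.3.3 already gives. With the reference corrected to 4.3.4, it is the 4.3.4 analysis, already given there.

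**4. Appendix 2.** Its listed changes point to SAP 4.1, 4.4.1.2, 4.6, 4.5.1 and 4.5.2. None points to 4.3.5.

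**5. How large the effect could be (illustration only)**

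The plan's own figure first (SAP Section 2: SD 1.1, margin 0.3, true difference 0, one-sided 2.5%, power 90%):

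n per arm = 2 × (1.96 + 1.2816)² × 1.1² / 0.3² = 282.5, so 283 per arm and 566 in total. With 10% dropout, 283 / 0.9 = 314.4, so 315 per arm and 630 in total. Both agree with the SAP.

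The documents give no rescue rate, no off-drug rate and no per-protocol set size. Assume 283 per arm, SD 1.1 and a true on-treatment difference of 0.3:

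SE = 1.1 × √(2/283) = 0.0925

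P(upper 95% bound < 0.3) = Φ((0.3 − d)/SE − 1.96), where d is the expected difference with post-event values kept.

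| Assumption | d | P |
|---|---|---|
| No effect of the retained values | 0.300 | 2.5% |
| Difference erased in 10% of patients: 0.3 × (1 − 0.10) | 0.270 | 5.1% |
| Difference erased in 20%: 0.3 × (1 − 0.20) | 0.240 | 9.5% |
| Difference halved in 20%: 0.3 × (1 − 0.20 × 0.5) | 0.270 | 5.1% |
| Rescue lowers HbA1c by 0.5; 10% in each arm | 0.300 | 2.5% |
| Same; Gla-300 20%, IDeg-100 10%: 0.3 − 0.5 × 0.10 | 0.250 | 7.8% |
| Same; Gla-300 10%, IDeg-100 20%: 0.3 + 0.5 × 0.10 | 0.350 | 0.6% |

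With a smaller set of 250 per arm (also assumed), SE = 0.0984, and the two full-erasure rows become 4.9% and 8.9%.

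**The case against.** The strongest reply is that this is a broken cross-reference, not a chosen method. Section 4.3.5 declares itself supportive of estimand 1b, and Table 3, note b, already treats post-event data as missing for that estimand. Protocol Table 8-3 puts the per-protocol analysis in the estimand 1b row, where such data are excluded, although that entry sits under main estimation. The phrase about the primary analysis echoes the protocol's ANCOVA sentence. A programmer could reasonably take the model from 4.3.3 and the data rule from estimand 1b. This is a plausible account of the intention, but it has to be inferred: the section's only explicit instruction leads to a model with no exclusion.

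Second, the main check on rescue and stopping is elsewhere. SAP 4.1 says that if non-inferiority holds without superiority, support comes from the supplementary estimand as described in 4.3.4, which is correctly specified in the full ITT set. This stands. A reader might infer that the non-inferiority conclusion is compromised, but that decision rests on 4.3.2, and 4.3.4 applies the exclusion.

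Third, the contents of the per-protocol set are less certain than they look. The deviation rules document is not available. SAP Table 8 lists insulins as a prohibited category without a stated exception for rescue, while protocol 5.2.2 names prandial insulin as a possible preferred rescue; these passages must be reconciled. It follows that the set does not reliably remove post-event data, not that all of it stays.

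Fourth, the SAP did not create the gap. The protocol's per-protocol ANCOVA states no exclusion either. This also stands.

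**Conclusion.** The point holds as a mismatch between an analysis and its stated estimand. As written, 4.3.5 supports a hypothetical estimand with a model that applies no hypothetical data rule, and the per-protocol definition does not reliably supply one. The SAP carried this gap forward from the protocol, mislabelled 4.3.3 as the primary analysis, and changed the model without listing the change.

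A reader might infer that the retained values must dilute the difference and make non-inferiority too easy to support. The documents do not establish that. If Gla-300 is worse and is rescued more, the bias is towards no difference; this is plausible, because rescue is triggered by high FPG or HbA1c. With equal rescue rates and equal effects there is none, and with more rescue on IDeg-100 it reverses. The figures from 0.6% to 9.5% rest on assumed event rates, effects and set size. They are not error rates of a planned test either, because 4.3.5 reports estimates and intervals with no pass or fail rule.

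The practical reach is limited. The trial was terminated on 27 June 2023, before the SAP was approved on 17 October 2023, and the abbreviated report's output list (SAP 5.6) has no per-protocol or MMRM efficacy output. Reported results do not change.

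**What to change.** In SAP 4.3.5:

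- Replace the reference to 4.3.3 with the MMRM of 4.3.4, and remove the description of it as the primary analysis.
- State that HbA1c after discontinuation of study drug or after rescue is excluded, and that the model is fitted in the per-protocol set.
- Drop the ITT repeat.

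In SAP Appendix 2, list the change from the protocol's per-protocol ANCOVA to an MMRM.

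The cost is a few lines of SAP text. The model is already specified in 4.3.4, no new data are needed, and the sample size of 566 evaluable and 630 randomized is unchanged.
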